3.3 Treatment variables

The subject level treatment variable TRT30P represents the randomised (planned) treatment for the period "treatment" and can be found in the ADSL dataset.

In all other ADAM datasets, the record level treatment variable, TRTP is used. TRTP should be non-missing showing randomised treatment.

The values of the individual treatment variables are given in Table 6.

Table 6Values for treatment variables

Treatment variable	Pre-specified values (based on naming from previous trials)
ARM	Liraglutide 1.8 mg, OAD
TRT30P/ TRTP	Lira 1.8 mg, OAD
TRTPN	1, 2

Note that ARM is defined as "Label" in the MMA and TRT30P is defined as "Short label" in MMA.

CONFIDENTIAL

Date:

Version:

Status:

Page:

10 September 2019 | Novo Nordisk 1.0 Final 14 of 42

3.4 Subject issues that require special analysis rules

This section should include descriptions of any situation that affects the analysis of an individual subject and how it was handled. A sub-section should only be included in case a violation in the given subsection is done

Guidance to handling violations is given below:

3.4.1 Subjects receiving wrong treatment

The subject receiving treatment different than from the randomised treatment will be included in his randomised treatment arm for efficacy analysis and in the treatment received arm for safety analysis.

The subject randomised in OAD arm and switching to a different OAD during the course of trial will be considered in the OAD he started with after randomisation for all analyses.

3.4.2 Subjects randomised but not exposed to trial product

The subjects are included in the full analysis set, but excluded from safety analysis set (SAFFL='N'), and in e.g. the ADAE dataset there will not be any events in the treatment period.

3.4.4 Subjects switching sites

Subjects switching sites will keep their original subject ID and site and will be analysed accordingly.

3.5 Use of visit windowing, unscheduled visits, and record selection

The analysis flag ANELFL is used to define records selected for summaries and analyses. E.g. if several measurements exist for a parameter at a visit then ANELFL will be 'Y' for the measurement used for analysis and ' ' for the other measurements. The variable ANELREA will be filled in with a description for all ANELFL=' ' and kept empty when ANELFL='Y'.

The ANELFL and ANELREA will be included in all datasets with visit structure (BDS datasets). The ANELFL is created before deriving other flags as e.g. baseline flag to ensure only one baseline measurement for a given parameter.

3.5.1 Visit windowing or reallocation

Visit reallocation will not be performed. All data will be used for all analyses.

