Attend visit fasting		х		х		х		х				х	

Protocol	UTN: U1111-1170-7035	Date:	04 September 2015	Status:	Final	Novo Nordisk
Trial ID: NN2211-4232	EudraCT no.: 2015-002417-29	Version:	1.0	Page:	11 of 67	

Trial Periods	Screening ¹	Random isation					Trea	tment				End of treatment	Follow up
Visit type	S	S	P/S ²	S	s	s	s	s	S	S	s	S	Р
Visit number	1	2	3	4	5	6	7	8	9	10	11	12	13
Timing of visit, Weeks	Up to -2	0	2	4	16	26	38	52	65	78	91	104	105
Visit window, Days			±7	±4	±10	±10	±10	±10	±10	±10	±10	±4	+4
Systolic and diastolic blood pressure, sitting		х		х	х	х	х	х	х	х	х	х	
Pulse, sitting		х		х	х	х	х	х	х	х	х	х	
Handout diary and instruct in use ⁵		х		х	х	х	х	х	х	х	х		
Handout blood glucose meter and instruct in use		х											
Prescription of trial product		х		х	х	х	х	х	х	х	х		
Information about trial product handling		х	$(\mathbf{x})^4$										
Drug accountability				х	х	х	х	х	х	х	х	х	
Adverse events		Х	х	х	х	х	х	х	х	х	х	х	х
Hypoglycaemic episodes		х	х	х	х	х	х	х	х	х	х	х	х
Technical complaints			х	х	х	х	х	х	х	х	х	х	
End of treatment												х	
End of trial													Х
Sign off Casebook													х

Abbreviations: IWRS: Interactive web response system; P/S: Phone contact/Site visit; S: Site visit; P: Phone contact

¹ Procedures and assessments relating to visit 1 may be conducted at visit 2 prior to randomisation. Trial related procedures (including requesting the subject to be fasting) are not allowed before signing of informed consent

² Visit 3 can be performed as either a phone contact or a site visit at the discretion of the investigator.

³ Subjects withdrawing from the trial should attend end of treatment visit as soon as possible.

Protocol Trial ID: NN2211-4232 UTN: U1111-1170-7035 EudraCT no.: 2015-002417-29

Date: 04 Sep Version:

04 September 2015 | Status: 1.0 | Page: Final Novo Nordisk 12 of 67

⁴ Information about and training in trial product handling to be given at the discretion of the investigator.

⁵ Diaries should be reviewed at every visit. Relevant data should be reported into the eCRF.

CONFIDENTIAL

Date: Version: Status: Page:

3 Background information and rationale for the trial

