5.5 Treatment after discontinuation of trial product

Subjects meeting any withdrawal criteria must be withdrawn from the trial and stop treatment with trial product. After trial discontinuation the investigator is responsible for further treatment of the subject. Novo Nordisk will not provide or reimburse treatment after trial discontinuation.

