8.1.5 Withdrawals

If a subject is withdrawn from the trial, the investigator must aim to undertake procedures similar to those for visit 12 as soon as possible if acceptable to the subject. The end-of-trial form must be completed, and final drug accountability must be performed even if the subject is not able to come to the trial site. In addition the follow-up telephone contact (visit 13) should be completed approximately 1 week after the early treatment discontinuation visit if possible. After that the case book must be signed.

Although a subject is not obliged to give his/her reason(s) for withdrawing from a trial, the investigator must make a reasonable effort to ascertain the reason(s), while fully respecting the subject's rights. Where the reasons are obtained, the primary reason for not completing the trial must be specified on the end-of-trial form in the eCRF.

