The main statistical analyses and summaries will be based on assessments taken while the subject is on treatment. With exception for AEs (see Section 17.4.1.2), the period in which a subject will be considered to be on treatment extends to one day after last administration of trial product.

Laboratory values below the lower limit of quantification (LLOQ) will be set to ½LLOQ.

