17.4 Secondary endpoints

17.4.1 Supportive secondary endpoints

17.4.1.1 Efficacy endpoints

Time to premature treatment discontinuation (for any reason including inadequate glycaemic control)

Protocol Trial ID: NN2211-4232 UTN: U1111-1170-7035 EudraCT no.: 2015-002417-29

CONFIDENTIAL

Date: Version: Status: Page:

The time to premature treatment discontinuation will be analysed using the same type of generalised log rank test as for the primary endpoint with the difference that subjects who discontinue treatment before 104 weeks without having an event of inadequate glycaemic control will not be considered as censored but as meeting the endpoint. For these discontinued subjects, the event will be considered to have occurred in the interval between the last attended visit on treatment and the next planned visit.

Change from baseline in HbA_{1c} at 104 weeks or at premature treatment discontinuation

The change from baseline in HbA_{1c} will be evaluated using an analysis of covariance (ANCOVA) model where the last post-baseline measurement taken on treatment will enter as the dependent variable, treatment arm and country as factors and baseline HbA_{1c} as a covariate. The estimated differences between Victoza[®] and OAD will be presented together with the corresponding 95% confidence intervals and two-sided p-values.

To further describe the effects of Victoza[®] compared to OAD with respect to the change from baseline in HbA_{1c}, supportive analyses will be performed using a mixed model for repeated measurements (MMRM) where all post-baseline measurements taken on treatment will enter as the dependent variable, treatment arm as a factor and baseline HbA_{1c} as a covariate. The factor and the covariate will be nested within visit. An unstructured covariance matrix for the measurements within subject will be employed. From this analysis, the differences between Victoza[®] and OAD at different visits will be estimated.

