2.3.3 On-treatment period

In accordance with protocol on-treatment definition as follows: the on-treatment period is defined as the observations occurring from when subject initiates randomised treatment (treatment start date) to

- Efficacy parameters, safety lab and hypos: 1 day after last dose of randomised treatment (both days included)
- AEs: 7 days after last dose of randomised treatment (both days included)

For missing date of last dose see section 3.6.1.

For subjects in the safety analysis set (SAFFL = "Y"), the baseline assessments (ABLFL = "Y") in the in-trial period (INTRFL = "Y") will be included in the on-treatment period (ONTRTFL = "Y").

The variable ONTRTFL are used to define periods on-treatment. ONTRTFL will be 'Y' for all records in the period on-treatment and 'N' at other periods. The ONTRTFL will be included in all datasets with visit structure (BDS).

3 Analysis considerations related to multiple analysis datasets

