3.6.12 Time-to-event endpoints

3.6.12.1 Primary endpoint - Time to inadequate glycaemic control

The primary endpoint is the time to inadequate glycaemic control defined as $HbA_{1c} > 7.0\%$ (53 mmol/mol) at two scheduled consecutive visits after first 26 weeks of treatment and up to 104 weeks. First possible occurrence is at week 38.

The data will inherently be interval censored, since HbA_{1c} is only measured at the scheduled visits while subjects may reach an $HbA_{1c} > 7.0\%$ at any time between 2 visits. The possible failure times will be viewed as continuous variable which can only be observed to lie in the interval between the visit when the treatment failure is established and the previous scheduled visit.

In order to perform the analysis, interval (t1, t2] will be identified where t1 is the time of the last visit at which an event has not occurred for the subject and t2 is the time of the visit at which the event occurs.

HbA_{1c} records will be extracted from the laboratory analysis dataset (ADHBA1C) with a selection on non-missing measurements which were taken while on treatment at the scheduled visits 5, 6, 7, 8, 9, 10, 11 and 12 which correspond to weeks 16, 26, 38, 52, 65, 78, 91 and 104.

The first post-baseline HbA1c assessment was done at visit 5 (Week 16). However, for determining consecutive visits, assessments from visit 6 onwards will be considered.

Visits with only non-missing measurements of HbA_{1c} will be considered to determine whether visits are consecutive or whether a visit is the last visit on treatment. For example, if there are HbA_{1c} measurements at visit 6 and visit 8 but it is missing at visit 7, then visit 6 and 8 will be considered as two consecutive visits.

The interval (t1, t2] will be identified as below.

1) If the subject discontinued treatment before Week16, subject is censored with t1 as time of visit at Week 0 and t2 as missing.

Statistical Program. Specification		Date:	10 September 2019	Novo Nordisk
Trial ID: NN2211-4232	CONFIDENTIAL	Version:	1.0	
UTN: U1111-1170-7035	CONFIDENTIAL	Status:	Final	
EudraCT No: 2015-002417-29		Page:	22 of 42	

- 2) If the subject discontinued treatment between Week 16 and Week 26, then subject is censored with t1 as time of visit at Week 16 and t2 as missing.
- 3) If the subject does not have any non-missing HbA_{1c} measurements on treatment, subject is censored with t1 as time of visit at Week 0 and t2 as missing.

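### With no visit reallocation, early end-of-treatment samples can enter the supportive by-visit MMRM as week-104 values, unless a rule outside these documents labels them otherwise

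*SAP*

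**What the plan says.** **Early leavers and visit 12.** Footnote 3 of the protocol flow chart (section 2) states: "Subjects withdrawing from the trial should attend end of treatment visit as soon as possible". Protocol 8.1.5 adds that "the investigator must aim to undertake procedures similar to those for visit 12 as soon as possible". The flow chart has one end-of-treatment column, visit 12 at week 104 (window ±4 days), and it includes HbA1c, FPG, body weight and blood pressure.

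**Visit labels in the analysis.** SAP 3.6.12.1 lists "scheduled visits 5, 6, 7, 8, 9, 10, 11 and 12 which correspond to weeks 16, 26, 38, 52, 65, 78, 91 and 104". SAP 3.5.1 states: "Visit reallocation will not be performed. All data will be used for all analyses". SAP 4.2.1 nevertheless names visit reallocation among the steps that decide whether a record is eligible for analysis.

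**What enters the MMRM.** Under protocol 17.4.1.1, "all post-baseline measurements taken on treatment will enter as the dependent variable", with treatment and baseline nested within visit. The stated purpose is the effect that would have been seen had all subjects stayed on treatment and completed all visits. The same supportive analyses are planned for FPG, body weight, BMI and blood pressure.

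**On-treatment limit.** Protocol section 17 says that "the period in which a subject will be considered to be on treatment extends to one day after last administration of trial product", and SAP 2.3.3 agrees. Protocol 5.5 says: "Subjects meeting any withdrawal criteria must be withdrawn from the trial and stop treatment with trial product".

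**The concern.** A by-visit model estimates each visit's treatment difference from the values filed under that visit. Suppose a subject withdrawn at week 38 gives an end-of-treatment sample that is filed as visit 12. The week-104 cell then holds a week-38 response, and the model treats an early leaver as observed at week 104 when that value should be missing.

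None of the safeguards in the documents catches this. The rule of one record per subject per visit (SAP 4.2.1) keeps the sample, because a withdrawn subject has only one visit-12 record. SAP 5.2.10 excludes only unscheduled and non-visit laboratory records. The list of exclusion reasons in Appendix B.1 has no entry for an early end-of-treatment sample.

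At stake are the week-104 estimates of the supportive by-visit models. The MMRM is the only planned analysis aimed at the effect had everyone stayed on treatment. In a trial that expects most subjects to leave before week 104, even a modest share of misfiled samples carries weight in that cell.

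**Working it through.** **Inputs.** Protocol 17.1 and Amendment 1, item 2.11: 1994 randomised; 20% per arm (200) leave without inadequate control; Victoza mean 6.9%; OAD mean steps from 6.9% to 7.2% after week 65; SD 0.85%. Allocation is 1:1. Withdrawal follows two consecutive values above 7.0% from week 26 (protocol 6.4). Values are taken as independent between visits, because that setting reproduces the plan's event rates.

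**Plan's figures first.**
- Followed after week 26: 997 × 0.8 = 797.6 per arm.
- Chance of a value above 7.0%: 1 − Φ(0.1/0.85) = 0.453 at mean 6.9%, and Φ(0.2/0.85) = 0.593 at mean 7.2%.
- Event probabilities at weeks 38, 52, 65, 78, 91, 104: Victoza 0.2054, 0.1123, 0.1123, 0.0892, 0.0766, 0.0640 (total 66.0%); OAD 0.2054, 0.1123, 0.1123, 0.1168, 0.1312, 0.0816 (total about 76%). The plan states 66% and 76%.
- Completers: 1994 − 400 − 526 − 606 = 462, as stated.
- A log-rank drift calculation needs 2026 subjects for 90% power, against 1994 (1.6% apart).

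**Who could supply a visit-12 value.** Withdrawn for inadequate control at weeks 38–91: 475.2 Victoza and 540.7 OAD, about 1016 in all. Reaching week 104: 322.4 and 256.9, about 579 in all.

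**Week-104 estimate when a share f of early samples is on treatment and filed as visit 12.** Each early sample is taken as a fresh draw at the mean of its own time. Of the 540.7 OAD leavers, 163.8 + 89.6 + 89.6 = 343.0 left at mean 6.9% and 93.1 + 104.7 = 197.8 left at mean 7.2%. The Victoza mean is 6.9% throughout, so

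difference(f) = 0.30 × (256.9 + 197.8f) / (256.9 + 540.7f).

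| f (assumed) | Calculation | Difference |
|---|---|---|
| 0% | 0.30 × 256.9/256.9 | 0.30 |
| 5% | 0.30 × 266.8/283.9 | 0.28 |
| 10% | 0.30 × 276.7/311.0 | 0.27 |
| 25% | 0.30 × 306.4/392.1 | 0.23 |
| 50% | 0.30 × 355.8/527.3 | 0.20 |
| 100% | 0.30 × 454.7/797.6 | 0.17 |

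Large-sample maximum-likelihood fits with arm-by-visit means and unstructured covariance agree. They move by at most about 0.01 for within-subject correlations up to 0.6.

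**Against sampling error.** With no early values the SD of the estimate is 0.85 × √(1/322.4 + 1/256.9) = 0.071. At f = 25% the arms hold 441.2 and 392.1 values, the standard error is about 0.059 and the bias is 0.30 − 0.234 = 0.066, or 1.1 standard errors. A nominal 95% interval then covers 0.30 in about 80–81% of trials. At f = 5% the loss of coverage is slight.

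**Sensitivity.**
- Adding the roughly 200 per arm who leave before week 26, at the same share: 0.27, 0.25, 0.21, 0.17 and 0.14 at 5, 10, 25, 50 and 100%.
- Early sample only repeats the confirming value: 0.29–0.30 at 5% and 0.26–0.27 at 25%.
- Constant difference, fresh draws: no bias.
- Difference fading from 0.30 to 0.10: 0.11–0.14 at 5% and 0.16–0.19 at 25%, so the week-104 effect is overstated.

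**The case against.** The strongest reply is that the deciding link is not in the documents. No section says that an early sample is stored under visit 12. Protocol 8.1.5 asks for similar procedures and refers to the contact as an early discontinuation visit, which would fit a separate label. Visit numbering belongs to the eCRF and the PSPS, and SAP 1.1 says that the SAP records only deviations from and additions to the PSPS. This stands, and it makes the point conditional. It does not remove it: 3.5.1 is an explicit rule against reallocation, and nothing visible supplies the missing label.

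Second, few early samples may count as on treatment, since subjects meeting a withdrawal criterion must stop trial product and the window is one day. This also stands, and at a 5% share the error is only about 0.02. The share need not be near zero, however. HbA1c is measured centrally (protocol 8.4), so the confirming result may arrive after the visit while the subject is still taking product.

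Third, the SAP's primary-endpoint rules place early leavers by when treatment stopped or the last value was taken, which suggests that the authors do not think of early samples as week 104. That is fair, but those rules do not govern the MMRM. It is also true that using all data cannot be literal, because off-treatment, non-fasting FPG and unscheduled laboratory records are dropped. None of those exclusions reaches an on-treatment visit-12 record.

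A reader might infer that the trial's week-104 results are mostly mislabelled early values, or that the effect is bound to be diluted. The documents support neither. The first needs visit-12 storage and a high on-treatment share, and the direction depends on how the true difference develops.

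**Conclusion.** The concern holds as a conditional one. On the visible text, an early on-treatment sample can be analysed as a week-104 value in the by-visit MMRM, against that model's stated aim, and SAP 3.5.1 and 4.2.1 do not agree on reallocation.

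Its reach is limited to the week-104 estimates of the supportive by-visit models for HbA1c, FPG, body weight, BMI and blood pressure. The ANCOVA and responder endpoints use the last on-treatment value by design and are not harmed. The primary endpoint is not affected in the plan's scenario.

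The size rests on three assumptions: storage as visit 12, the on-treatment share, and the plan's late step in the OAD mean. Under these, a true 0.30 becomes about 0.28 at a 5% share and 0.23–0.24 at 25%. Since neither the share nor the course of the difference is known in advance, a reader of the results could not correct for the error. Importance: between a minor clarification and a change that should be made.

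**What to change.** In SAP 3.5.1, flag early end-of-treatment samples by actual date and keep them out of the week-104 cell of the by-visit MMRM for all five endpoint groups. In the planning model this returns 0.30. An alternative is to assign each sample to the planned visit whose window it falls in; that would need a rule for samples outside every window and for visits that already hold a value.

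Excluding the values is a departure from the protocol 17.4.1.1 rule on which data enter the MMRM, and should be recorded as such. State that the same values remain eligible as the last on-treatment value for the ANCOVA and responder endpoints. Align 3.5.1 with 4.2.1. If a PSPS rule already does this, citing it is enough.

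The cost is one derivation step in the HbA1c, laboratory and vital-sign datasets, and the loss of some early on-treatment values from the week-104 cell. No new data are needed.

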3.5.2 Re-test

See PSPS version 1.0 for general rules.

For the following assessment tests and re-tests the subjects are required to be fasting according to the protocol:

• Fasting plasma glucose (FPG) at visits: 2, 4, 6, 8, and 12

If these assessments are taking with fasting status 'Not fasting' the values are considered not valid (ANELFL = '').

3.6 Imputation and derivation methods

All imputations of AVAL are indicated in the variable DTYPE at record level in all ADaM datasets.

3.6.1 Date imputations

Date and time are captured in the ISO 8601 format in SDTM and follows the pattern:

yyyy-mm-ddTHH:MM:SS.

Table 8Date variables and related imputation methods

Description	Variable	Imputation flag	Imputation method
Treatment start date	TRTSDT	TRTSDTF	Actual date of first trail product
			administration or Randomisation date,
			whichever comes later
Treatment end date	TRTEDT	TRTEDTF	Actual date of last trial product
			administration or Date of last visit in
			on-treatment period or Date of last
			trial-related subj-site contact,
			whichever comes first
Medical history/	Start	ASTDTF	MONTH: Jan
concomitant illness			DAY: 1 st
			A missing start year will not be
			imputed, but for medical history the
			event will be classified to belong to
			the Screening
	Stop	AENDTF	If continuing="No"
			MONTH: Dec
			DAY: Last day of month.
			If imputed date is after randomisation
			then Date of randomisation-1 will be
			used
Concomitant	Start	ASTDTF	MONTH: Jan
medication			DAY: 1 st
			If imputed date is before
			randomisation then the Date of
			randomisation will be used
	Stop	AENDTF	If continuing="No"
	_		MONTH: Dec
			DAY: Last day of month.
			If imputed date is after last day in trial
			then Date of last trial-related subj-site
			contact will be used
Adverse events	Start	ASTDTF	1 st of month.
			If imputed date is before TRSTDT
			then TRSTDT date will be used
	Stop	AENDTF	Last day of month.
			If imputed date is after last day in trial
			then Date of last trial-related subj-site
			contact will be used
			If "not recovered" then AENDTF=""

Statistical Program. SpecificationTrial ID: NN2211-4232UTN: U1111-1170-7035EudraCT No: 2015-002417-29	ENTIAL Date: Version: Status: Page:	10 September 2019 1.0 Final 17 of 42	Novo Nordisk
---	--	---	--------------

Hypoglycaemic	Start	ASTDTF	DAY: 1st unless:
events/			(1) Event stop date is non-missing
Hyperglycaemic			where Start date will be stop date -
Events			1
			(2) Event occurs in same month as
			TRSTDT, in which case TRSTDT
			is used
			TIME: 00:00
			Event date is the same as first drug
			date then time will be time of first
			drug intake, if possible, or 24:00
	Stop	AENDTF	DAY: The day after hypo start date
			TIME: 24:00

For all date variables that can be imputed (listed in Table 8) the imputation flag can take values "" (blank), D, M and Y and are set as described below. The imputation flag variable is only included if any dates/times are imputed.

Table 3.1.3.1	Some Exa	mples of	f Setting	of Date	Imputa	tion Flag

Missing Elements	SDTMDTC String	ADaM Date Value (*DT Variable) ^[1,2] (## indicates imputed portion)	Imputation flag (*DTF variable)	
None	YYYY-MM-DD	YYYY-MM-DD	Blank	
Day	YYYY-MM	YYYY-MM-##	D	
Month	YYYYDD	YYYY-##-DD	М	
Month and Day	YYYY	YYYY-##-##	М	
Year	MM-DD	####-MM-DD	Y	
Year and Month	DD	####-##-DD	Y	
Year and Month and Day		####-##	Y	
[1] The ISO formats used in the ADaM Date Value column are for the purposes of illustration, and are not intended to imply any type of display standard or				
requirement. The DT variable is numeric and the producer will determine the appropriate display format.				
[2] The indication of imputed values is not intended to imply an imputation rule or standard. For example, if the month is missing, imputation rules might				
specify that the collected day value be ignor	ed so that both month and d	av are imputed.		

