2.3 Section 6.2 Inclusion criteria

4. Stable daily dose of metformin as monotherapy \geq 1500 mg or maximum tolerated dose within *for* \geq 60 days prior to the screening visit.

Protocol Amendment 1		Date:	30 May 2016	Novo Nordisk
Trial ID: NN2211-4232	CONFIDENTIAL	Version:	1.0	
UTN: U1111-1170-7035	CONFIDENTIAL	Status:	Final	
EudraCT No.: 2015-002417-29		Page:	4 of 6	

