5.2.4 ADCM - Concomitant medication analysis

The ADCM contains all collected concomitant medication observations in SDTM.CM from randomised subjects. Information from SDTM.SUPPCM and SDTM.TS is added.

The continuation flag (CONTINFL) indicating if the concomitant medication is ongoing or not, relative to the treatment period, is set as "Y" when CM.CMENRF is equal to "ONGOING" otherwise it is set to blank.

The status relative to screening date (ASCRF) is set as "COMPLETED BEFORE" when analysis start date (ASTDT) and analysis end date (AENDT) is less than the screening date. ASCRF is set as "STARTED AFTER" when ASTDT is greater than the screening date. Finally, ASCRF is set as "ONGOING" when ASTDT is less or equal to the screening date and AENDT is greater or equal to the screening date or missing.

The status relative to baseline (ABLRF) is set as "COMPLETED BEFORE" when analysis start date (ASTDT) and analysis end date (AENDT) is less than the randomisation date (ADSL.RANDDT). ABLRF is set as "STARTED AFTER" when ASTDT is greater than the randomisation date. Finally, ABLRF is set as "ONGOING" when ASTDT is less or equal to the randomisation date and AENDT is greater than or equal to the randomisation date.

When AENDT is greater than or equal to the last visit date, ACRF or ABLRF is set to "ONGOING" based on ASTDT and AENDT is set to missing.

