Appendix B Good Specification Practice for Data Derivations

B.1 Sequence of ANELREA text:

The ANELREA text is prioritized in the following order:

- 1. "Unscheduled assessment"
- 2. "Assessment not planned"
- 3. "Record at baseline visit was excluded due to date after treatment start"
- 4. "Before in-trial observation period"
- 5. "After in-trial observation period"
- 6. "No measurement"
- 7. "Record was excluded due to subject being non-fasting"
- 8. "Retest rule 1: Not first value for visit"
- 9. "Assessment done after starting add on glucose lowering drug"

The ANELREA enters all BDS ADaM datasets.

CONFIDENTIAL

Date: Version: Status: Page:

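### SAP Table 8 moves partial concomitant-medication start dates up to randomisation even when the recorded year or month is clearly pre-trial, so background metformin can be labelled as started after screening

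*SAP*

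**What the plan says.** **Imputation rule.** In SAP 3.6.1, Table 8, the concomitant-medication start row sets a missing month to January and a missing day to the 1st. It then adds a condition that opens "If imputed date is before" and continues "randomisation then the Date of" randomisation is to be used. The medical-history start row of the same table has no such floor. The adverse-event start row has one, but to the treatment start date.

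**Status variables.** SAP 5.2.4 derives two variables from the resulting start date (ASTDT) and the stop date (AENDT):
- ASCRF, relative to screening, is STARTED AFTER "when ASTDT is greater than the screening date". It is ONGOING if the start is on or before screening and the stop is on or after screening or missing. It is COMPLETED BEFORE if both dates precede screening.
- ABLRF, relative to baseline, uses the same three classes with the randomisation date as reference. Its ONGOING rule does not mention a missing stop.

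**Dates and data.** SAP 5.2.1 sets the randomisation date to the date of visit 2. Protocol 5.1 allows up to 2 weeks of screening, and footnote 1 of the flow chart allows visit 1 procedures to be done at visit 2. Inclusion criterion 4, as amended (Amendment 1, 2.3), requires a stable metformin dose for at least "60 days prior to the screening visit". Protocol 8.2.2 has diabetes medication recorded at the first visit, with start and stop dates.

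**Record selection.** SAP Appendix B.1 lists, as reason 9 for leaving a record out of analysis, "Assessment done after starting add on glucose lowering drug".

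**The concern.** A floor at randomisation makes sense for a drug known to have begun during the trial whose exact date is incomplete. It does not make sense for a drug whose recorded year or month shows that it began long before. Table 8 treats the two alike, so it overwrites information that was collected.

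Two things are at stake. First, the screening status of background treatment comes out wrong: metformin, which every eligible subject must already be taking, can appear as newly started. Second, traceability suffers. SAP 3.6.1 illustrates an imputation flag based on which elements were missing. If the flag is set that way, a year-only record is marked as having its month imputed, although the year has been replaced as well.

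**Working it through.** No sample-size or power figure is involved. The check applies the two SAP rules to example records, with and without the floor.

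**Inputs.** Start-date rule from SAP Table 8; ASCRF and ABLRF rules from SAP 5.2.4; randomisation date = visit 2 (SAP 5.2.1); screening-to-randomisation gap of 0 to 14 days (Protocol 5.1 and flow chart footnote 1). The calendar dates are illustrative assumptions: screening 2017-03-01, randomisation 2017-03-15 (gap 14 days). A missing stop is read as ongoing for ABLRF.

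| Record | Floor | ASTDT | ASCRF | ABLRF |
|---|---|---|---|---|
| Metformin, start 2012, continuing | as written | 2017-03-15 | STARTED AFTER | ONGOING |
| Same | none | 2012-01-01 | ONGOING | ONGOING |
| Drug, start 2015, stop 2017-03-10 | as written | 2017-03-15 (after stop) | STARTED AFTER | no category |
| Same | none | 2015-01-01 | ONGOING | COMPLETED BEFORE |
| Drug, start 2015, stop 2017-02-01 | as written | 2017-03-15 (after stop) | STARTED AFTER | no category |
| Same | none | 2015-01-01 | COMPLETED BEFORE | COMPLETED BEFORE |

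**Why no ABLRF category fits.** Take the last drug with the floor. ASTDT equals the randomisation date, so it is neither before it (COMPLETED BEFORE fails) nor after it (STARTED AFTER fails). AENDT is before randomisation, so ONGOING fails.

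**Size of the date error.** A start recorded as 2012 truly lies between 2012-01-01 and 2012-12-31. From 2012-01-01 to 2017-03-15 is 1,827 + 73 = 1,900 days; from 2012-12-31 it is 1,900 − 365 = 1,535 days. The moved date is therefore 1,535/365.25 = 4.2 to 1,900/365.25 = 5.2 years too late.

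**Where the error stops.**
- Gap of 1 day: same ASCRF and ABLRF classes as in the table.
- Gap of 0 days: metformin is ONGOING on both variables, so no error. A drug stopped before screening still gets a start after its stop.
- Year-month start (2012-06): same classes as year-only. Complete start date: unaffected.
- Order of metformin start against assessments, gap of 14 days: those at weeks −12 and −2 now precede the start, which is reversed; visit 2 ties with it; weeks 4 to 104 are unchanged.

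**Add-on drugs, a separate mechanism.** A glucose-lowering add-on recorded only as 2017 imputes to 2017-01-01, and the floor lifts it to 2017-03-15. If it truly began months into treatment, the imputed start is too early because of the 1 January rule; the floor brings it closer to the truth. Whether this matters for record selection depends on which date reason 9 uses, and the SAP does not say. SAP 3.5 fills the reason text only for records left out, and SAP 4.2.1 runs date imputation before the selection flag, so a link is possible. Against it, the list of inputs to that flag in 4.2.1 does not name add-on medication, and Table 14 lists the HbA1c dataset ahead of the medication dataset.

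**The case against.** The strongest reply is that this is a labelling defect in one dataset and that nothing important depends on it. Much of that stands:

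- A reader might infer that HbA1c values are lost and the primary result affected. The documents do not show this. SAP 3.6.12.1 takes non-missing on-treatment HbA1c at scheduled visits, and SAP 2.3.3 defines on-treatment from trial-product dosing. Neither cites a concomitant-medication date. Appendix B.1 is a priority order for reason texts, so loss of values is conditional on an unstated choice of date.
- A reader might infer that background drugs are out of order against the whole trial. Only pre-randomisation assessments and the tie at visit 2 are affected, and baseline status is correct.
- A reader might infer that subjects who change drug are misidentified. They are handled by Protocol 6.4 (criterion 4) and the censoring rule in Protocol 17.3, not by an imputed date.
- Eligibility is judged at the site before randomisation. The derived label conflicts with criterion 4 but does not undo anyone's eligibility. Protocol 8.2.4 also has current diabetes treatment recorded separately.
- Protocol 8.2.2 defines concomitant medication as taken during the trial, including screening, so a drug stopped before screening may seldom be recorded. SAP 5.2.4 nevertheless provides a class for such records, and a drug stopped during screening is within the definition.
- The project-level specification and the table shells are not available. No medication-at-screening table can be confirmed, and general handling rules may exist there. SAP 1.1 says, however, that this document gives the deviations from and additions to that specification, so Table 8 has to be read as the trial's rule.

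The reply does not rescue the rule. For the records it covers, the output conflicts with collected data and can have an impossible date order.

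**Conclusion.** Wrong as written. With screening at least one day before visit 2, every continuing drug whose partial start imputes to before randomisation but truly began before screening is set to STARTED AFTER instead of ONGOING. A drug with such a start that stopped before randomisation gets a start after its stop and no ABLRF class.

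The certain harm is to concomitant-medication classification and traceability. No effect on the primary endpoint is shown. Possible exclusion of valid on-treatment values is a separate, conditional point: it arises only if reason 9 uses the imputed start, and its cause is the January/1st imputation of a partially dated add-on, not the floor.

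The number of affected records is unknown. If a share of 10 to 30% partial metformin dates were assumed, 0.10 × 1994 = 199 to 0.30 × 1994 = 598 subjects would have such dates, before removing those screened and randomised on the same day. Nothing in the documents supports any such share, so this range is not an estimate.

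The conclusion assumes that Table 8 is applied literally and, for ABLRF, that a missing stop means ongoing. The last sentence of SAP 5.2.4, which resets drugs running to the last visit to ONGOING, is ambiguous; because it works from the start date, it does not clearly repair ASCRF.

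**What to change.** Amend the concomitant-medication start row of SAP Table 8:

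1. Apply the randomisation-date floor only when the recorded part of the date is compatible with a start on or after randomisation and the drug was not already reported at visit 1 or 2. The floor then never overwrites a recorded year or month.
2. Otherwise keep the imputed pre-randomisation date.
3. Never let an imputed start exceed the stop date.
4. For a glucose-lowering add-on first reported after visit 2 with a partial start, use the latest of randomisation, the 1st of the known month, and the day after the last visit at which it was not reported.
5. State in Appendix B.1 that reason 9 uses this date and does not apply to background metformin.

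In the same edit, state in SAP 5.2.4 that a missing stop counts as ongoing for ABLRF, as it already does for ASCRF.

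The cost is a few lines of text and one derivation. No new data are needed, because the flow chart has concomitant medication reviewed at every visit and Protocol 8.2.2 has changes recorded as they occur. The downside is slightly more programming, to use the visit at which each drug was first reported.
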